9.2.5 Study Follow-up

The registry will record data abstracted from medical charts. Data will be abstracted from the date the patient had a cinacalcet prescription recorded within the study observation period and will continue until death, lost-to-follow-up, transfer to another centre that is not a participating in this registry, turns age 18-years, withdrawal of consent, or end of the study period (ie, 31 December 2023), whichever comes first. Regardless of whether the patient discontinued cinacalcet, follow-up will continue until one of the events described above occurs.

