9.3.2 Outcome Assessment

Baseline

- Demographics (sex, age at cinacalcet initiation)
- Medical history (underlying renal disease and presence of comorbidities, HNF1 β mutation, history of parathyroidectomy, history of kidney transplant,; and history of hypocalcaemia)

Observation period (spans from baseline to end of study follow-up)

- Dialysis treatment (switch dialysis modality and dialysis discontinuation)
- Cinacalcet use (prevalent or incident user, cinacalcet type (Mimpara or generic), length of cinacalcet use (*prevalent user only*), date of prescription, prescribed dose, dosage forms (tablets or capsules), frequency, length of prescription, date of prescription change, type of prescription change (dose change, drug withheld, drug discontinuation), reason for prescription change (dose titration, non-compliance, adverse event, nausea, vomiting, PTH-low, PTH-high, PTH within target, hypocalcaemia, hypercalcemia, haemodialysis discontinued, parathyroidectomy, kidney transplant, patient refusal, safety finding, product complaint, other)
- Concomitant medication use (phosphate binders (eg, Calcium carbonate/Calcium acetate, Sevelamer, Lanthanum carbonate, sucroferric oxyhydroxide), oral calcium supplementation, vitamin D (eg, Vitamin D3, active vitamin D analogue), dietary calcium intake, rHGH in terms of dose, frequency, route of administration, date first taken, and date last taken)
- Laboratory parameters (PTH, total Ca, ionized Ca, serum phosphorus, albumin, alkaline phosphatase, bicarbonate (HCO₃), 25OH-Vitamin D3 and HNF1 β mutation); and local PTH clinical target and assay range and cCa level definition of hypocalcaemia)
 - Incidence of hypocalcaemia will be identified in two ways: occurrence of laboratory value reporting cCa < 2.1 mmol/L; or reported adverse event due to hypocalcaemia (ie, blood cCa decreased or symptomatic hypocalcaemia)
 - Medical events of parathyroidectomy and kidney transplant(if kidney transplant, additional laboratory parameters, calcinuria, urine calcium/creatinine ratio, and renal ultrasounds will be collected)
 - Physical measurements (height, weight before and after dialysis, vital signs (systolic and diastolic blood pressure before dialysis), Tanner stage)

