9.7.2.3.2 Description of Patient Characteristics

Demographics and baseline characteristics (specified in [Section 9.3.2](#)) of patients who initiate cinacalcet and patients who develop and do not develop hypocalcaemia will be summarised.

Treatment characteristics (sHPT medications) at time of first cinacalcet use (*'incident cohort'*) or on 28 August 2017 (*'prevalent cohort'*) will be summarised.

PTH, Ca, P and other relevant laboratory parameters will be described by plotting the median and IQR values every month (30 days) or three months (90 days) following index date and following hypocalcaemia event. Data will be presented overall and stratified by levels of control (eg, low, medium or high of Ca values or mild, moderate or severe PTH levels) at baseline or following hypocalcaemia event (mild, moderate and severe hypocalcaemia) to show the longitudinal trajectory of laboratory values.

To describe time-to-event of first hypocalcaemia event (*incident cinacalcet cohort only*), cinacalcet discontinuation (*incident cinacalcet cohort only*) and cinacalcet re-initiation, KM curves will be plotted, and KM estimates will be calculated. Patients will be censored if they had a kidney transplant, parathyroidectomy or experienced one of the follow-up events ([section 9.2.5](#)), whichever comes first. In the time to hypocalcaemia event analysis, patients will also be censored if they discontinued cinacalcet.

To describe risk factors associated with time to first hypocalcaemia event (*incident cinacalcet cohort only*) after cinacalcet initiation, a multivariate Cox model will be used.

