9.7.2.4 Analysis of the Primary Endpoint(s)

Demographics and baseline characteristics (specified in [Section 9.3.2](#)) of patients who initiate cinacalcet and patients who develop and do not develop hypocalcaemia will be summarised.

Treatment characteristics (sHPT medications) at time of first cinacalcet use (*'incident cohort'*) or on 28 August 2017 (*'prevalent cohort'*) will be summarised.

PTH, Ca, P and other relevant laboratory parameters will be described by plotting the median and IQR values every month (30 days) or three months (90 days) following index date and following hypocalcaemia event. Data will be presented overall and stratified by levels of control (eg, low, medium or high of Ca values or mild, moderate or severe PTH levels) at baseline or following hypocalcaemia event (mild, moderate and severe hypocalcaemia) to show the longitudinal trajectory of laboratory values.

To describe time-to-event of first hypocalcaemia event (*incident cinacalcet cohort only*), cinacalcet discontinuation (*incident cinacalcet cohort only*) and cinacalcet re-initiation, KM curves will be plotted, and KM estimates will be calculated. Patients will be censored if they had a kidney transplant, parathyroidectomy or experienced one of the follow-up

events ([section 9.2.5](#)), whichever comes first. In the time to hypocalcaemia event analysis, patients will also be censored if they discontinued cinacalcet.

To describe risk factors associated with time to first hypocalcaemia event (*incident cinacalcet cohort only*) after cinacalcet initiation, a multivariate Cox model will be used.

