9.9.1.2 Information Bias

Information bias is unlikely to affect the findings of this study unless participating sites record exposures and/or outcomes more diligently for patients treated with cinacalcet compared to nephrology centres not participating in the study. It is possible that hospitalised patients may artificially appear to be non-persistent (ie, discontinued) as new prescriptions may not be issued until they return to their nephrology centre. If this is the case, then time-varying analyses would identify hospitalisation as a risk factor, although it should be acknowledged that it would be impossible to determine if this is a true (worsening clinical condition) or artificial effect. However, we anticipate this occurrence to be low as most acute complications are managed in the paediatric nephrology unit where they are normally cared for.

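### The Kaplan-Meier curves censor at death, transplant, parathyroidectomy and (for hypocalcaemia) treatment stop, so 1-KM is not the probability that patients actually have hypocalcaemia or stop cinacalcet

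*Protocol*

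**What the plan says.** Protocol 9.7.2.3.2 and 9.7.2.4 carry the same text. Kaplan-Meier curves and estimates are planned for first hypocalcaemia and for cinacalcet discontinuation (both in incident users only) and for re-initiation. For all three: "Patients will be censored if they had a kidney transplant, parathyroidectomy or experienced one of the follow-up events". The follow-up events are those of 9.2.5 and include death. For hypocalcaemia there is one more rule: "In the time to hypocalcaemia event analysis, patients will also be censored if they discontinued cinacalcet". A multivariate Cox model for first hypocalcaemia follows.

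Four other places bear on this:

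- 9.2.5 keeps patients under observation after a stop: "Regardless of whether the patient discontinued cinacalcet, follow-up will continue until one of the events described above occurs". 9.3.1 confirms that laboratory abstraction carries on unchanged.
- 9.3.2 lists reasons for a prescription change, among them "hypocalcaemia, hypercalcemia, haemodialysis discontinued, parathyroidectomy, kidney transplant, patient refusal". A change may be a dose change, a withholding or a discontinuation, and its type and date are recorded. Transplant and parathyroidectomy are also recorded separately as medical events.
- 9.7.3 sends the summary of hypocalcaemia incidence to 9.7.2.4.
- The sensitivity analyses in 9.7.2.5 vary only the definition of hypocalcaemia, and 9.7.2.5.3 marks sensitivity analysis for bias as not applicable.

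**The concern.** Use of cinacalcet and incidence of hypocalcaemia are both primary objectives (8.1). A reader of the final report will naturally take the height of a 1-KM curve at one year as the share of children who had the event by then. Under this censoring it is not.

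- **Competing events.** Each censored patient is treated as still able to have the event at the same rate as those who remain. The curve answers what would happen if nobody died, was transplanted, had a parathyroidectomy or stopped.
- **Stops linked to the outcome.** 9.3.2 lists adverse event, vomiting, low PTH and hypocalcaemia as reasons for a change, and 9.3.1 gives stopping because of hypocalcaemia as an example. A stop after a recorded event does no harm, because the event is counted first. A stop for tolerability or calcium concerns before a value below 2.1 mmol/L is drawn removes a patient who may be at raised risk. Blood draws follow routine practice (9.1), so the confirming value can come after the stop and is then left out of this analysis.
- **Discontinuation.** A stop caused by transplant or parathyroidectomy may be censored rather than counted, depending on which date comes first.

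**Working it through.** **The plan's own figure.** 9.5 gives a 95% half-width of 10.1% at n = 70 and incidence 25%. The Wald formula gives 1.96 × √(0.25 × 0.75 / 70) = 10.14%, which agrees. That figure is for a simple proportion and is unaffected by this point. The protocol states no figure for the curves.

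**Inputs**

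- Event hazard h = 0.645 per year, from 64.5 per 100 subject-years in the earlier paediatric trials (7.2), treated as constant.
- Alternative h = −ln(1 − 0.25) = 0.288 per year, reading the 25% planning incidence of 9.5 as a 1-year risk. The protocol attaches no time to it, so this is an assumption.
- Exit hazard c (stop, transplant, parathyroidectomy and death combined): not in the protocol. Assumed 0.1 to 1.0 per year.

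**Hypocalcaemia, exits independent of the event**

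1-KM = 1 − exp(−ht)

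Cumulative incidence before any exit = h/(h + c) × [1 − exp(−(h + c)t)]

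For example, with h = 0.645, c = 0.4 and t = 1: 1-KM = 1 − exp(−0.645) = 47.5%; cumulative incidence = 0.645/1.045 × [1 − exp(−1.045)] = 40.0%.

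| h, time | 1-KM | c = 0.1 | 0.2 | 0.4 | 0.6 | 1.0 |
|---|---|---|---|---|---|---|
| 0.645, 1 year | 47.5% | 45.5% | 43.5% | 40.0% | 36.9% | 31.6% |
| 0.645, 2 years | 72.5% | 67.1% | 62.2% | 54.1% | 47.5% | 37.7% |
| 0.288, 1 year | 25.0% | 23.8% | 22.8% | 20.8% | 19.1% | 16.2% |

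The 1-year gap is 2.0 to 15.9 points at h = 0.645 and 1.2 to 8.8 points at h = 0.288.

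**Hypocalcaemia, stops that pre-empt the event.** Suppose a share q of impending events is censored by a stop just beforehand. The curve then shows 1 − exp(−h(1 − q)t). With h = 0.645 at 1 year, q = 0.1 gives 44.0% and q = 0.3 gives 36.3%, against 47.5% with none pre-empted. This is 3.5 to 11.2 points in the other direction. The values of q are assumed.

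**Discontinuation.** Assume stops for other reasons at 0.5 per year and transplant or parathyroidectomy, each also ending cinacalcet, at 0.3 per year. At 2 years:

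- 1-KM with transplant and parathyroidectomy censored: 1 − exp(−1.0) = 63.2%
- all-cause discontinuation: 1 − exp(−1.6) = 79.8%
- probability of stopping for another reason first: 0.5/0.8 × 79.8% = 49.9%

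The planned curve matches neither quantity.

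**The case against.** Censoring at treatment stop is a standard on-treatment choice. Under independent exits the Kaplan-Meier estimate is unbiased for the risk it targets, so the first table compares two different quantities and does not demonstrate bias. The same censoring is right for a cause-specific hazard, including the planned Cox model. The objectives are descriptive, 9.5 sizes the study on a simple proportion, and 9.7.2.4 also summarises patients with and without hypocalcaemia, so the curves need not be the only answer on incidence. Further sensitivity analyses may appear in the SAP (9.7, 9.7.2.5.4). All of this stands. It does not remove the point: the protocol itself fixes the censoring rule, does not label the result as on-treatment and names no estimate of actual risk.

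Three stronger readings are tempting but not supported:

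- **Admission artefact.** A reader might infer from 9.9.1.2 that hospitalised patients would be censored during the very admission in which hypocalcaemia is recorded. That section expects such apparent stops to be infrequent. 9.9.1.1 uses prescribed days to define persistence, and 9.7.2.4 does not say that the curves use prescription gaps.
- **Transplant frequency.** A reader might assume that transplant is frequent enough to put the gap at the top of the range. The protocol gives no transplant rate.
- **Reason codes.** A reader might infer that the coded reason decides whether a transplant counts as an event or a censoring. The listed reasons are for any prescription change, and transplant is recorded separately. What matters is the order of the dates, which the protocol leaves open when they coincide.

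**Conclusion.** The point holds as a matter of what the curves estimate. For any non-zero exit rate, 1-KM for hypocalcaemia exceeds the cumulative incidence before exit: by about 2 to 16 points at 1 year with h = 0.645 and about 1 to 9 points with h = 0.288, for assumed exits of 0.1 to 1.0 per year. Stops that anticipate hypocalcaemia push the curve down, so its net direction as a guide to the risk of hypocalcaemia is unknown. It should not be described as biased upward by a known amount.

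The discontinuation curve understates all-cause discontinuation wherever stops due to transplant or parathyroidectomy are censored: 63.2% against 79.8% in the example. It would be wrong to call it simply too high because 63.2% exceeds 49.9%; that holds only against the probability of stopping first for another reason.

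The sizes rest on constant hazards and assumed exit rates. The 0.645 comes from short exposure: 19/0.645 = 29.5 subject-years over about 19/0.24 = 79 subjects, or 0.37 years each. It also counts reported adverse events, whereas the registry counts laboratory values too. The Cox model is not at fault. The change is a worthwhile, cheap improvement.

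**What to change.** In 9.7.2.3.2 and 9.7.2.4:

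1. Label the existing hypocalcaemia Kaplan-Meier and Cox analyses as on-treatment (cause-specific), and state that 1-KM is not the actual risk.
2. Add Aalen-Johansen cumulative incidence with death, transplant and parathyroidectomy as competing events, and discontinuation as a further competing event for the on-treatment estimate.
3. Add a hypocalcaemia analysis not censored at discontinuation, using the laboratory follow-up already collected under 9.2.5 and 9.3.1.
4. Report all-cause discontinuation with its cause-specific components, showing transplant and parathyroidectomy separately. Take stops from the recorded type and date of prescription change, with a rule for coinciding dates.

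The cost is some wording and a few extra outputs, with no new data. The analysis in item 3 mixes on-drug and off-drug time, and 9.3.1 says treatment data end at first discontinuation while also foreseeing re-initiation. The report should state that limit.

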9.7.2.5 Sensitivity Analysis

The analysis of hypocalcaemia may be repeated using total serum Ca thresholds. In addition, the analysis of hypocalcaemia may be repeated by each of the following definitions of hypocalcaemia: 1) according to cCa levels only 2) as a reported adverse event (ie, blood decreased cCa or symptomatic hypocalcaemia) or 3) according local site cCa definition of hypocalcaemia

9.7.2.5.1 Subgroup Analysis

Not applicable

9.7.2.5.2 Stratified Analysis

The following stratified analyses may be performed:

- Hypocalcaemia will be grouped by low (2.1- < 2.5 mmol/L), medium (2.5- < 2.75 mmol/L) and high (\geq 2.75 mmol/L) normal cCa levels at baseline cinacalcet
- Hypocalcaemia may be stratified by severity, mild, moderate and severe (as defined in [section 9.7.2.4](#))
- Incidence of hypocalcaemia will be stratified by cinacalcet dosage forms: tablet < 30mg (ie, crushed tablet), tablet \geq 30 mg or capsules.
- Incidence of hypocalcaemia will be stratified by occurrence in retrospective vs. prospective data collection

9.7.2.5.3 Sensitivity Analysis for Residual Confounding and Bias

Not applicable.

9.7.2.5.4 Other Sensitivity Analysis

Other sensitivity analyses may be conducted to meet country-specific regulatory requirements. Details will be specified in the SAP.

9.7.3 Analysis of Safety Endpoint(s)/Outcome(s)

The incidence of hypocalcaemia will be summarised as described in [section 9.7.2.4](#).

9.8 Quality Control

Source data verification will be performed at the study site, in accordance with Amgen standard operating procedures (SOPs).

The investigator is to maintain a list of appropriately qualified persons to whom he/she has delegated study duties. All persons authorized to make entries and/or corrections on eCRFs will be included on the Amgen Delegation of Authority Form.

Source documents are original documents, data, and records from which the patient's eCRF data are obtained. These include but are not limited to hospital records, clinical and office charts, laboratory and pharmacy records, diaries, microfiches, radiographs, and correspondence.

The investigator and study staff are responsible for maintaining a comprehensive and centralized filing system of all study-related (essential) documentation, suitable for inspection at any time by representatives from Amgen and/or applicable regulatory authorities. Documents to be maintained for the study are as follows:

- patient files containing the completed eCRF, informed consent forms, as applicable, and patient identification list
- study files containing the protocol with all amendments, copies of prestudy documentation, and all correspondence to and from the Independent Ethics Committee (IEC) or other relevant ethical review board and Amgen

In addition, all original source documents supporting entries in the eCRFs must be maintained and be readily available. Retention of study documents will be governed by the contractual agreement with Amgen.

Amgen retains all data, programs, and outputs generated for the study. At study close, data are uploaded from the Medidata Rave database and stored in accordance with Amgen SOPs. Statistical programming and outputs are locked in the analysis environment and no updates are permitted; standard programming procedures will apply.

9.9 Limitations of the Research Methods

9.9.1 Internal Validity of Study Design

9.9.1.1 Measurement Error(s)/Misclassification(s)

Persistence of medications is quantified by the number of days the medication is available to the patient. This represents a simplified measure, since the definition does not access if the patient takes the medication (ie, compliance/adherence). Nonetheless, in the absence of a valid measure and to maintain consistency and comparability between studies of persistence, the number of days the medication was prescribed to the patient during his/her observation period in this study will be used as a proxy to define persistence.

Hypocalcaemia event is defined by cCa laboratory value and reporting of adverse event due to hypocalcaemia (ie, blood cCa decreased or symptomatic hypocalcaemia). It is possible that hypocalcaemia may be under-reported if a patient did not have both albumin and total serum Ca measured on the same day to calculate cCa. However, we may assume that for those circumstances, hypocalcaemia events (if any occurred) are likely to be asymptomatic. For symptomatic hypocalcaemia events, which result in hospitalisation or medical interventions, these events will be captured as an adverse event.

9.9.1.2 Information Bias

Information bias is unlikely to affect the findings of this study unless participating sites record exposures and/or outcomes more diligently for patients treated with cinacalcet compared to nephrology centres not participating in the study. It is possible that hospitalised patients may artificially appear to be non-persistent (ie, discontinued) as new prescriptions may not be issued until they return to their nephrology centre. If this is the case, then time-varying analyses would identify hospitalisation as a risk factor, although it should be acknowledged that it would be impossible to determine if this is a true (worsening clinical condition) or artificial effect. However, we anticipate this occurrence to be low as most acute complications are managed in the paediatric nephrology unit where they are normally cared for.

9.9.1.3 Selection Bias

Patients included in the study represent paediatric patients who receive maintenance dialysis and are treated at nephrology centres participating in the IPDN or ESCAPE networks. The study may not be representative of the paediatric population receiving cinacalcet at nephrology centres that are not participating in these paediatric nephrology networks.

9.9.1.4 Confounding

As with all observational studies, residual confounding is plausible if relevant confounding factors (eg, data known to inform treatment decisions) were not collected and cannot be considered in adjusted analyses. In addition, confounding by indication is also plausible if patients who are treated with other sHPT medications (eg, vitamin D) are inherently different from those who are treated with cinacalcet, eg, if one group is more likely to have severe sHPT (high PTH levels) than the other.

9.9.2 External Validity of Study Design

As with all observational studies, residual confounding is plausible if relevant confounding factors (eg, data known to inform treatment decisions) were not collected and cannot be considered in adjusted analyses. In addition, confounding by indication is also plausible if patients who are treated with other sHPT medications (eg, vitamin D) are inherently different from those who are treated with cinacalcet., eg, if one group is more likely to have severe sHPT (high PTH levels) than the other.

9.9.3 Analysis Limitations

The precision of estimates will depend on the number of sHPT patients treated with cinacalcet.

9.9.4 Limitations Due to Missing Data and/or Incomplete Data

Key variables are those expected to be recorded in routine clinical care of paediatric CKD dialysis patients and missing/incomplete data recorded in the patient's medical records is therefore not anticipated or limited.

9.10 Other Aspects

Not applicable.

10. Protection of Human Subjects

This study will comply with all relevant ethical and regulatory requirements in each country and will not be used for the conduct of marketing surveys or other marketing purposes. The study will comply with Amgen adverse event reporting SOPs. This study and data collection will be conducted in accordance with the relevant local laws.

The responsible physician is also responsible for sending the following documents to Amgen or its representative for review before study initiation occurs:

- Signed and dated protocol signature page (Responsible Physician's Agreement)
- Copy of the Central Ethics Board approval of the protocol, waiver for requirement of informed consent where applicable
- Patient or patient's legally acceptable representative has provided informed consent (for countries where required per local regulations)
- Up-to-date curriculum vitae of responsible physician and all co/sub-physicians
- Signed confidentiality agreement
- Signed study contract

The responsible physician will be charged with maintaining correct and comprehensive documentation, while the Amgen monitor/designee is tasked to ensure that the responsible physician is following the correct study protocol.

